7.2.9.2 Dose Modification

Pembrolizumab will be withheld for drug-related Grade 4 haematological toxicities, and non-haematological toxicity \geq Grade 3 including laboratory abnormalities, and severe or life-threatening AEs as per Table 8 below.

In case toxicity does not resolve to Grade 0-1 within 12 weeks after last infusion, trial treatment should be discontinued after consultation with the Sponsor. With Investigator and Sponsor agreement, patients with a laboratory AE still at Grade 2 after 12 weeks may continue treatment in the trial only if asymptomatic and controlled. For information on the management of AEs, see Section 6 and Table 8.

Patients who experience a recurrence of the same severe or life-threatening event at the same grade or greater with re-challenge of pembrolizumab should be discontinued from trial treatment.

Events of Clinical interest (ECI) can be potential irAEs and dose modifications for these toxicities should they occur can be found in Appendix 5.

Dosing interruptions are permitted in the case of medical / surgical events or logistical reasons not related to study therapy (e.g., elective surgery, unrelated medical events, patient vacation, and/or holidays). Subjects should be placed back on study therapy within 3 weeks of the scheduled interruption, unless otherwise discussed with the Sponsor. The reason for interruption should be documented in the patient's study record.

Table 8: Dose modification guidelines for drug-related adverse events.

Toxicity	Hold Treatment for Grade	Timing for Restarting Treatment	Treatment Discontinuation
Diarrhoea/Colitis	2-3	Toxicity resolves to Grade 0-1/baseline.	Toxicity does not resolve within 12 weeks of last dose or inability to reduce corticosteroid to 10 mg or less of prednisone or equivalent per day within 12 weeks.
	4	Permanently discontinue	Permanently discontinue
AST, ALT, or Increased Bilirubin	2	Toxicity resolves to Grade 0-1	Toxicity does not resolve within 12 weeks of last dose.
	3-4	Permanently discontinue (see exception below) ¹	Permanently discontinue
Type 1 diabetes mellitus (if new onset) or Hyperglycemia	T1DM or 3-4	Hold pembrolizumab for new onset Type 1 diabetes mellitus or Grade 3-4 hyperglycemia associated with evidence of beta cell failure.	Resume pembrolizumab when patients are clinically and metabolically stable.

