	4	Permanently discontinue	Permanently discontinue
Confirmed Stevens-Johnson Syndrome or Toxic-epidermal Necrolysis	-	Permanently discontinue	Permanently discontinue
All Other Drug-Related Toxicity ²	3 or Severe	Toxicity resolves to Grade 0-1	Toxicity does not resolve within 12 weeks of last dose or inability to reduce corticosteroid to 10 mg or less of prednisone or equivalent per day within 12 weeks.
	4	Permanently discontinue	Permanently discontinue

Note: Permanently discontinue for any severe or Grade 3 drug-related AE that recurs or any life-threatening event.

¹ For patients with liver metastasis who begin treatment with Grade 2 AST or ALT, if AST or ALT increases by greater than or equal to 50% relative to baseline and lasts for at least 1 week then patients should be discontinued.

² Patients with intolerable or persistent Grade 2 drug-related AE may hold study medication at physician discretion. Permanently discontinue study drug for persistent Grade 2 adverse reactions for which treatment with study drug has been held, that do not recover to Grade 0-1 within 12 weeks of the last dose.

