7.4.1.5 Management of infusion reactions

Acute infusion reactions (which can include cytokine release syndrome, angioedema, or anaphylaxis) are different from allergic/hypersensitive reactions, although some of the manifestations are common to both AEs. Signs and symptoms usually develop during or shortly after drug infusion and generally resolve completely within 24 hours of completion of infusion. Signs/symptoms may include: Allergic reaction/hypersensitivity (including drug fever); Arthralgia (joint pain); Bronchospasm; Cough; Dizziness; Dyspnoea (shortness of breath); Fatigue (asthenia, lethargy, malaise); Headache; Hypertension; Hypotension; Myalgia (muscle pain); Nausea; Pruritus/itching; Rash/desquamation; Rigors/chills; Sweating (diaphoresis); Tachycardia; Tumour pain (onset or exacerbation of tumour pain due to treatment); Urticaria (hives, welts, wheals); Vomiting. Table 9 below shows treatment guidelines for patients who experience an infusion reaction associated with administration of pembrolizumab.

7.5 Supportive Care Guidelines for Immune-related Adverse Events (irAE) and Immune-related Events of Clinical Interest (irECI)

Immune-related Adverse Events (irAEs) may be defined as an AE of unknown aetiology, associated with drug exposure and is consistent with an immune phenomenon. irAEs may be predicted based on the nature of the pembrolizumab compound, its mechanism of action, and reported experience with immunotherapies that have a similar mechanism of action. Special attention should be paid to AEs that may be suggestive of potential irAEs. An irAE can occur shortly after the first dose or several months after the last dose of treatment. If an irAE is suspected, efforts should be made to rule out cancer, infectious, metabolic, toxin or other etiologic causes prior to labelling an AE as an irAE. Patients who develop a Grade 2 or higher irAE should be discussed immediately with the Chief Investigator or delegate.

Recommendations to managing irAEs not detailed elsewhere in the protocol are detailed in Table 10.

Table 9: Infusion Reaction Treatment Guidelines

CTCAE Grade	Treatment	Premedication at subsequent dosing
Grade 1 Mild reaction; infusion interruption not indicated; intervention not indicated	Increase monitoring of vital signs as medically indicated until the patient is deemed medically stable in the opinion of the investigator.	None

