irAE	Withhold/Discontinue Pembrolizumab?	Supportive Care
Grade 1	No action	Provide symptomatic treatment
Grade 2	May withhold pembrolizumab. For recurrent grade 2 pneumonitis, pembrolizumab should be discontinued permanently.	Consider systemic corticosteroids in addition to appropriate symptomatic treatment. Steroid taper should be considered once symptoms improve to Grade 1 or less and tapered over at least 4 weeks. Based on limited data from clinical studies in subjects whose immune-related adverse reactions could not be controlled with corticosteroid use, administration of other systemic immunosuppressants can be considered.
Grade 3 and Grade 4	Withhold pembrolizumab Discontinue if unable to reduce corticosteroid dose to < 10 mg per day prednisone equivalent within 12 weeks of toxicity	Systemic corticosteroids are indicated in addition to appropriate symptomatic treatment. May utilize 1 to 2 mg/kg prednisone or equivalent per day. Steroid taper should be considered once symptoms improve to Grade 1 or less and tapered over at least 4 weeks. Based on limited data from clinical studies in subjects whose immune-related adverse reactions could not be controlled with corticosteroid use, administration of other systemic immunosuppressants can be considered.
Please Note: If an irAE does not resolve or improve to \leq Grade 1 within 12 weeks after last administration of pembrolizumab, study therapy discontinuation should be considered after discussion with a Merck Clinical Director via the RM-CTU trial manager.		

Details for managing specific irAEs are summarised below:

Immune-mediated pneumonitis

Monitor subjects for signs and symptoms of pneumonitis. If pneumonitis is suspected, evaluate with radiographic imaging and exclude other causes. Administer corticosteroids for Grade 2 or greater events (initial dose of 1-2 mg/kg/day prednisone or equivalent followed by a taper), withhold pembrolizumab for moderate (Grade 2) pneumonitis, and permanently discontinue pembrolizumab for recurrent moderate (Grade 2), severe (Grade 3) or life-threatening (Grade 4) pneumonitis.

Immune-mediated colitis

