Thyroid disorders have been reported in subjects receiving pembrolizumab and can occur at any time during treatment; therefore, monitor subjects for changes in thyroid function (at the start of treatment, periodically during treatment and as indicated based on clinical evaluation) and clinical signs and symptoms of thyroid disorders. Hyperthyroidism may be managed symptomatically. Withhold pembrolizumab for severe (Grade 3) hyperthyroidism, and permanently discontinue pembrolizumab for life-threatening (Grade 4) hyperthyroidism. Hypothyroidism may be managed with replacement therapy without treatment interruption and without corticosteroids. For subjects with severe (Grade 3) or life-threatening (Grade 4) endocrinopathy that improves to Grade 2 or lower and is controlled with hormone replacement, continuation of pembrolizumab may be considered.

Other immune-mediated AEs

The following additional clinically significant, immune-mediated adverse reactions were reported in less than 1% (unless otherwise indicated) of subjects treated with pembrolizumab: uveitis, myositis, Guillain-Barré syndrome, pancreatitis and severe skin reactions (1.1%).

In addition, a set of irAEs have also been classified as immune-related events of clinical interest (irECI) a full list of these can be found in Table 12 in section 8.5.2. Patients with symptomatic irECIs should immediately stop receiving pembrolizumab and be evaluated to rule out non-treatment related causes of the event. Overdose and liver toxicity irECIs irrespective of relationship to the study drug should be reported within 24 hours of the investigator being aware to the Sponsor (via RM-CTU) who will in turn notify MSD. If the irECI is determined to be associated please refer to Appendix 5 for the recommendations on the management of these irECIs. If the event is not considered to be associated with the study drug the physician should exercise individual clinical judgment on the event management based on the patient. Any additional questions of the collection or information on management of irECIs should be directed to the Sponsor (via RM-CTU).

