Ocular - (classified as ECI if \geq Grade 2 or any grade resulting in dose modification or use of systemic steroids to treat the AE)		
Uveitis	Iritis	
Renal - (classified as ECI for \geq Grade 2)		
Nephritis	Nephritis autoimmune	Renal Failure
Renal failure acute	Creatinine elevations - (report as ECI if \geq Grade 3 or any grade resulting in dose modification or use of systemic steroids to treat the AE)	
Skin - (classified as ECI for any grade)		
Dermatitis exfoliate	Erythema multiforme	Stevens-Johnson Syndrome
Toxic epidermal necrolysis		
Skin - (classified as ECI for \geq Grade 3)		
Pruritus	Rash	Rash generalised
Rash maculo-papular	Any rash clinical significant in the physicians judgement.	
Other - (classified as ECI for any grade)		
Myocarditis	Pancreatitis	Percarditis
Any other grade 3 event which is considered immune-related by the physician.		

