
Other:
 
 Pericarditis Pancreatitis Any additional Grade 3 or higher event which the physician considers to be immune related 	Grade 2 or Grade 1 that do not improve with symptomatic treatment.	
 Report overdose and liver toxicity ECIs within 24 hours Withhold Pembrolizumab Consider biopsy for confirmation of diagnosis. 	
 Systemic corticosteroids may be indicated. If so: Treat with systemic corticosteroids at a dose of 1 to 2 mg/kg prednisone or equivalent once per day. When symptoms improve to Grade 1 or less, steroid taper should be started and continued over no less than 4 weeks. Permanently discontinue for inability to reduce corticosteroid dose to 10 mg or less of prednisone or equivalent per day within 12 weeks. Otherwise, Pembrolizumab treatment may be restarted and the dose modified as specified in the protocol
	Grade 3	
 Withhold Pembrolizumab 	
 Treat with systemic corticosteroids at a dose of 1 to 2 mg/kg prednisone or equivalent once per day. When symptoms improve to Grade 1 or less, steroid taper should be started and continued over no less than 4 weeks. Permanently discontinue for inability to reduce corticosteroid dose to 10 mg or less of prednisone or equivalent per day within 12 weeks. Otherwise, pembrolizumab treatment may be restarted and the dose modified as specified in the protocol
	Grade 4	
 Discontinue pembrolizumab 	
 Treat with systemic corticosteroids at a dose of 1 to 2 mg/kg prednisone or equivalent once per day.

12.6 Appendix 6 – Modified Response Evaluation Criteria in Solid Tumours (mRECIST) Criteria for Evaluating Response in Malignant Pleural Mesothelioma

The modified RECIST criteria were developed by Byrne and Novak (2004). Tumour thickness perpendicular to the chest wall or mediastinum should be measured in two positions at three separate levels on transverse cuts of CT scan.

In this protocol, mRECIST for MPM criteria will be used to assess response to therapy as follows:

1. mRECIST for MPM criteria will be used for tumour response evaluation in sites of disease outside the radiotherapy field by 2 cm above and 2 cm below the margins of the irradiated volume.

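### For a grade 4 immune-related event with no row of its own, Table 10 says withhold pembrolizumab while the catch-all rows of Table 8 and Appendix 5 say discontinue, and no sentence ranks the three

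*Protocol*

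**What the plan says.** Three places give a general dosing action for an irAE that is not named individually.

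- **Section 7.5, Table 10.** Grades 3 and 4 share one row. The action is to withhold, with this condition for stopping: "Discontinue if unable to reduce corticosteroid dose to < 10 mg per day prednisone equivalent within 12 weeks of toxicity". A note under the table adds that discontinuation should be considered, after discussion, if the event has not improved to grade 1 or less within 12 weeks of the last dose. The scope sentence before the table reads: "Recommendations to managing irAEs not detailed elsewhere in the protocol are detailed in Table 10".
- **Section 7.2.9.2, Table 8.** The last row, for all drug-related toxicity not listed above it, holds treatment at grade 3 and permanently discontinues at grade 4. The note under the table reads: "Permanently discontinue for any severe or Grade 3 drug-related AE that recurs or any life-threatening event".
- **Section 12.5, Appendix 5.** The last row includes this class: "Any additional Grade 3 or higher event which the physician considers to be immune related". It withholds at grade 3 and discontinues at grade 4. Its grade 3 steroid condition is: "Permanently discontinue for inability to reduce corticosteroid dose to 10 mg or less of prednisone or equivalent per day within 12 weeks".

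Several sentences direct the reader to one table or another. Section 7.2.9.2 points to Table 8 for dose modification, and to Appendix 5 for events of clinical interest that may be irAEs. Section 6.3.2 sends adverse events of possible immunological cause to Appendix 5. Section 7.4.1.4 sends the same class to Table 10 and a separate guidance document, without limiting this to events that lack detail elsewhere. For immune-related events of clinical interest, Section 7.5 says: "If the irECI is determined to be associated please refer to Appendix 5 for the recommendations on the management of these irECIs".

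**The concern.** Grade 4 is defined in Appendix 4 as life-threatening. Whether pembrolizumab is stopped for good or only held after such an event should not depend on which table the clinician opens. Myositis shows the gap. Section 7.5 lists it among the reported immune-mediated reactions but gives no action for it, and Table 8, Table 12 and Appendix 5 do not name it, so only the general rows apply.

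A clinician who follows Table 10 would hold treatment and wait for the steroid taper. One who follows Table 8 or Appendix 5 would stop. What is at stake is the safety of an individual patient and consistent handling across sites, not the trial's inference.

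**Working it through.** No arithmetic applies. The check sets the instructions side by side for a drug-related irAE without its own row, then asks whether the text ranks them.

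**Step 1: action by grade**

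| Source | Grade 3 | Grade 4 |
|---|---|---|
| Table 10, shared row | Withhold; discontinue if the steroid dose cannot be brought down within 12 weeks | Same as grade 3 |
| Table 8, catch-all row | Hold until grade 0–1 | Permanently discontinue |
| Table 8, note | Permanently discontinue on recurrence | Permanently discontinue (life-threatening) |
| Appendix 5, catch-all row | Withhold | Discontinue |

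At grade 3 all three sources withhold a first event. At grade 4, three instructions say discontinue (Table 8 row, Table 8 note, Appendix 5 row) and one says withhold (Table 10). The disagreement is therefore at grade 4 only.

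**Step 2: does the scope sentence settle it?** Table 10 covers irAEs not detailed elsewhere. There are two ways to read this.

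- If a catch-all row counts as detail elsewhere, the catch-alls already cover every drug-related irAE of grade 3 or 4, and the dosing column of Table 10's grade 3–4 row never decides anything.
- If a catch-all row does not count, Table 10 governs myositis and contradicts the catch-alls.

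Table 10 also does not keep to its stated scope: its grade 2 row carries a rule for recurrent pneumonitis, which Table 8, Table 11 and Appendix 5 already cover.

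**Step 3: do the cross-references settle it?** Section 7.2.9.2 and Section 6.3.2 favour Table 8 and Appendix 5. Section 7.4.1.4 sends the same class of event to Table 10 without a limit. No sentence says which table prevails.

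**Step 4: the steroid threshold.** Table 10 requires a dose below 10 mg, while Table 8 and Appendix 5 accept 10 mg or less. These differ only for a patient on exactly 10 mg. It is a wording mismatch to correct in the same edit.

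**The case against.** The best case on the other side is that the protocol, read as a whole, already points to stopping.

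- Dosing is assigned by the section titled Dose Modification to Table 8 and Appendix 5. Table 10 sits under supportive care, is called a general approach, and is residual by its own scope sentence. Its supportive-care column still has work to do on that reading.
- Withhold is not used as the opposite of discontinue. Section 7.2.9.2 says treatment is withheld for life-threatening events as set out in Table 8, and Table 8 then stops it. Withholding at onset breaches neither of the stricter tables.

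This stands to a large extent: the text leans towards discontinuation. It does not remove the conflict, because Section 7.4.1.4 gives an unlimited route to Table 10 and nothing ranks the tables.

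A reader might infer more than the documents support, in three ways.

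- **That Table 10 allows stopping only if the taper fails.** The row gives one condition for stopping and excludes no others, and its note adds a second ground to consider.
- **That the protocol permits re-dosing after such an event.** Table 10 has no restart clause. The words "recurrence of the same severe or life-threatening event at the same grade or greater with re-challenge of pembrolizumab" in Section 7.2.9.2 belong to a rule for stopping patients whose event recurs; they do not authorise re-challenge after a residual grade 4 irAE. Re-dosing is a possible consequence of following Table 10, not an instruction.
- **That grade 4 events fall outside Table 12 and so never reach Appendix 5.** The Table 12 entry reads "Any other grade 3 event which is considered immune-related by the physician", but it stands under a heading that classifies events at any grade, and Appendix 5 says grade 3 or higher. The wording is loose and does not establish an exclusion.

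**Conclusion.** The inconsistency is real and narrow. For a drug-related grade 4 irAE without its own row, Table 10 says withhold, with conditional discontinuation, and the catch-all rows of Table 8 and Appendix 5 say discontinue. The text leans towards discontinuation but does not say so outright.

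Severity is minor. The protocol gives no rate for such events, so no probability is calculated. Its only related figure is that myositis of any grade was reported in under 1% of pembrolizumab-treated subjects, and at most 18 patients are treated here. Section 7.5 requires irAEs of grade 2 or higher to be discussed immediately with the Chief Investigator or delegate. This lowers the risk, although that person consults the same tables. The dose-limiting toxicity rule, the sample size and the analyses are unaffected.

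The conclusion assumes that the event is judged drug-related and immune-related. It does not extend to events with their own rows. The separate guidance document named in Section 7.4.1.4 is not at hand and might give a ranking.

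**What to change.** Split the Table 10 row:

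- *Grade 3: withhold; discontinue if corticosteroid cannot be reduced to 10 mg or less prednisone equivalent per day within 12 weeks.*
- *Grade 4: permanently discontinue, except endocrinopathy controlled with hormone replacement (Section 7.5).*

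Add one sentence: *For pembrolizumab dosing, Table 8 and Appendix 5 take precedence over Table 10, with the same endocrinopathy exception.* The exception is needed because Section 7.5 lets treatment continue in that setting, whereas the Table 8 note would stop it for any life-threatening event.

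Optionally, change the Table 12 catch-all to grade 3 or higher, to match Appendix 5.

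The cost is one row split and one added sentence at the next amendment, plus two words if Table 12 is tidied. Design, sample size and data collection do not change. Expedited reporting under Section 8.5.2 still covers only overdose and liver toxicity among these events. The edit does not settle differences between Table 8 and Appendix 5 for named events such as hepatitis, which lie outside this point.

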7.6 Supportive Care Guidelines for Pneumonitis

Patients with symptomatic pneumonitis should immediately stop receiving pembrolizumab and have an evaluation. The evaluation may include bronchoscopy and pulmonary function tests to rule out other causes such as infection. If the patient is determined to have study drug associated pneumonitis, the suggested treatment plan is detailed in Table 11.

Table 11: Recommended Approach to Handling Pneumonitis

Study drug associated pneumonitis	Withhold/Discontinue Pembrolizumab?	Supportive Care
Grade 1 (asymptomatic)	No action	Intervention not indicated
Grade 2	Withhold pembrolizumab, may return to treatment if improves to Grade 1 or resolves within 12 weeks Second episode of pneumonitis – discontinue pembrolizumab if upon re-challenge the patient develops a second episode of Grade 2 or higher pneumonitis.	Consider pulmonary consultation with bronchoscopy and biopsy/BAL. Conduct an in person evaluation approximately twice per week Consider frequent Chest X-ray as part of monitoring Treat with systemic corticosteroids at a dose of 1 to 2 mg/kg/day prednisone or equivalent. When symptoms improve to Grade 1 or less, steroid taper should be started and continued over no less than 4 weeks. Consider antibiotics
Grade 3 and Grade 4	Discontinue pembrolizumab	Hospitalise patient Bronchoscopy with biopsy and/or BAL is recommended. Immediately treat with intravenous steroids (methylprednisolone 125 mg IV). When symptoms improve to Grade 1 or less, a high dose oral steroid (prednisone 1 to 2 mg/kg once per day or dexamethasone 4 mg every 4 hours) taper should be started and continued over no less than 4 weeks. If IV steroids followed by high dose oral steroids does not reduce initial symptoms within 48 to 72 hours, treat with additional anti-inflammatory measures. Discontinue additional anti-inflammatory measures upon symptom relief and initiate a prolonged steroid taper over 45 to 60 days. If symptoms worsen during steroid reduction, initiate a re-tapering of steroids starting at a higher dose of 80 or 100 mg followed by a more prolonged taper and administer additional anti-inflammatory measures, as needed add prophylactic antibiotics

	for opportunistic infections. The use of infliximab may be indicated as appropriate.
--	--

For Grade 2 pneumonitis that improves to \leq Grade 1 within 12 weeks, the following rules should apply:

- First episode of pneumonitis: May increase dosing interval by one week in subsequent cycles
- Second episode of pneumonitis: Permanently discontinue pembrolizumab if upon re-challenge the patient develops pneumonitis \geq Grade 2

